Full study protocol and statistical analysis plan

Official Title of the study:

Analyses of Interleukin-6, Presepsin and Pentraxin-3 in the diagnosis and severity of late-onset preeclampsia

Date of the document:

October 2019.

Contents:

1. Participant Flow
2. Baseline Characteristics
3. Outcome Measures
4. Endpoints of the study
5. Limitations and Strengths
6. Certain Agreements
7. Results Point of Contact

1. Participant Flow

Recruitment Details

The study was conducted at Cengiz Gokcek Women's and Children's Hospital, Gaziantep, Turkey at department of obstetric and gynecology between date of June 2018 and January 2019. The study protocol was designed according to the Declaration of Helsinki, and the institutional ethical review board of Gaziantep University approved the study (Reference number: 2018/393). The investigators included subjects consisted of women with a singleton pregnancy who were diagnosed as having late-onset preeclampsia between 34+0 and 41+0 weeks of gestation. Pregnant women with uncomplicated pregnancies were randomly selected to serve as controls. The study was conducted with 44 late-onset preeclampsia patients as study group and 44 patients with normal pregnancies as control group. All participants included in the study gave oral and written informed consent.

Pre-assignment Details

The authors firstly were assessed the recruited people to ensure meeting the inclusion and exclusion criteria.

The inclusion criteria were made according to the official documents.

Arm/Group Information *

There are two groups in the study.

Arm/Group Title *

Preeclampsia group

Control group

2. Baseline Characteristics

The normal distribution of data is analysed with Kolmogorov Smirnov ve Shapiro Wilk tests. Student t test was used for variables that normally distributed for group comparison(L-PrE/kontrol) and Mann Whitney U test was used for variables that is not normally distributed. Also, Sperasman correlation was used for relationship of non-normally distributed variables with each other. The ROC analysis was applied for determination of cut-off points for IL6, presepsin ve pentraxin-3 variables. SPSS for Windows 22.0 ve Medcalc programs were used for statistical analysis. P<0.05 was accepted as statistical significance.

3. Outcome Measures

Every participant in the study population underwent obstetric ultrasound examination and fetal-maternal assessment was carried out by one of the investigators. The obstetric anamnesis were obtained from all participants. The demographic data like age, gravidity, parity, body mass index (BMI) and gestational age were recorded. The gestational age was determined by calculation from the last menstrual period and supported by the ultrasonography measurements at first trimester of gestation. Maternal venous blood samples were taken for measurement of IL-6, presepsin and pentraxin-3 levels after the diagnosis of L-PrE in outpatient clinic. These samples quickly centrifuged at 1,500 g for 10 min, plasma samples were separated and stored at -80°C until the day of measurement. All patients with L-PrE were also hospitalized and their pregnancies were terminated. The samples of the control groups were obtained during the routine obstetrical care examination in the third trimester of pregnancy. Then these pregnant women were followed-up until the delivery. Both groups were compared in terms of maternal age, BMI, week of gestation, gravida, parity, live born, systolic/diastolic blood pressure, total protein in spot urine sample, hemoglobin, hematocrit, platelet count, white blood cell count, neutrophil, lymphocyte, neutrophil-to-lymphocyte ratio (NLR), urea, uric acid, albumin, blood urea nitrogen, creatinine, liver function tests (AST, ALT), lactic acid dehydrogenase, IL-6, presepsin, pentraxin-3, and infant weight at delivery. Neutrophil-to-lymphocyte ratio (NLR), which is the ratio of the neutrophils and lymphocytes in blood sample at admission, which can accept a marker of systemic inflammation. Small for gestational age (SGA) neonate was defined as birth weight <10th percentile for gestational age with Turkey's national nomogram as the reference for fetal growth. The maternal plasma presepsin levels were determined using a commercially available ELISA kit, the human presepsin ELISA Kit (Rel Assay Diagnostics, Gaziantep, Turkey), according to the manufacturer's instructions. Human presepsin ELISA kit is based on the principle of biotin double antibody sandwich technology. IL-6 levels in blood samples were measured by using the ELISA method (DIAsource ImmunoAssays SA, Nivelles, Belgium) in accordance with the method described by the manufacturer. Pentraxin-3 levels were measured by using the ELISA kits in accordance with the manufacturer's instructions (Sunredbio, Shanghai, PRC).

4. Endpoints of the study:

The primary endpoint in these analyses was IL-6, presepsin and pentraxin-3 levels in L-PrE group and control group.

The secondary endpoint was the IL-6, presepsin and pentraxin-3 levels in mild L-PrE group and severity L-PrE group.

Tertiary endpoint was the IL-6, presepsin and PTX-3 levels in SGA group and non-SGA group.

5. Limitations and strengths:

This study have some limitations. It was a small, observational and single-centered study. These three inflammatory markers were measured only during admission, we could not assess the changes in IL-6, presepsin, and pentraxin-3 in response to treatment due to lack of serial measurements.

We demonstrated, significant relations of all three elevated new inflammatory markers with both the presence and the severity of PrE at the same time in this study. Another strength of our study was that the women with PE had no pharmacological treatment. Because the antihypertensive drugs lead to the decrease in presepsin level due to the antiinflammatory effect.

6. Certain Agreements

The authors declare that they have no conflict of interest.

7. Results Point of Contact

Corresponding Author: [name], Cengiz Gokcek Public Hospital, Department of Obstetrics and Gynecology, Gaziantep/Turkey, [contact]

Address: [name]

GSM: [contact]

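### The ROC cut-offs appear to separate established late-onset preeclampsia from uncomplicated pregnancy; the title's diagnostic use goes further, and the limitations do not say so

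*Combined protocol and SAP*

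**What the plan says.** The title states the purpose as analysis of the markers "in the diagnosis and severity of late-onset preeclampsia". Section 1 (Recruitment Details) defines the cases as "women with a singleton pregnancy who were diagnosed as having late-onset preeclampsia between 34+0 and 41+0 weeks of gestation". For the comparison group it says "Pregnant women with uncomplicated pregnancies were randomly selected to serve as controls". The group sizes are 44 and 44.

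Section 3 adds that the cases' blood was drawn "after the diagnosis of L-PrE in outpatient clinic", while controls were sampled at routine third-trimester visits. Section 2 then says: "The ROC analysis was applied for determination of cut-off points for IL6, presepsin ve pentraxin-3 variables". It gives no groups for the ROC, no criterion for choosing a cut-off, and no confidence intervals.

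All three endpoints in section 4 are marker levels compared between groups: L-PrE versus control, mild versus severe L-PrE, and SGA versus non-SGA. Section 5 gives as limitations "It was a small, observational and single-centered study" and the lack of serial measurements.

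**The concern.** A diagnostic cut-off is applied to women in whom the disease is in question. The document describes no such women. One group already has the diagnosis, and the other is restricted to pregnancies without complications. A ROC curve from these two groups measures how well a marker separates known disease from normal pregnancy.

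Women who raise suspicion but turn out not to have preeclampsia may have marker levels above those of uncomplicated pregnancies. If so, more of them would exceed the cut-off than the study's controls did, and specificity and AUC in use would be lower than reported. Under this title, and with no such caution in section 5, readers could take the cut-offs as diagnostic thresholds.

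**Working it through.** **What can be checked.** The document gives no AUC, sensitivity, specificity, cut-off, SD or prevalence, so there is no figure to reproduce. The case share is 44/(44 + 44) = 50%. All inputs below are assumptions.

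**Effect of the control spectrum.** Assume normal markers with equal variance. Cases lie d SD above healthy controls, and non-cases with suspected disease lie m SD above healthy controls.

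- AUC against healthy controls = Φ(d/√2)
- AUC against suspected non-cases = Φ((d − m)/√2)
- With the cut-off at d/2, specificity is Φ(d/2) in healthy controls and Φ(d/2 − m) in suspected non-cases. Sensitivity is Φ(d/2) throughout.

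| d | m | AUC | Specificity at d/2 |
|---|---|---|---|
| 1.2 | 0 | Φ(0.849) = 0.80 | Φ(0.60) = 0.73 |
| 1.2 | 0.4 | Φ(0.566) = 0.71 | Φ(0.20) = 0.58 |
| 1.5 | 0 | Φ(1.061) = 0.86 | Φ(0.75) = 0.77 |
| 1.5 | 0.25 | Φ(0.884) = 0.81 | Φ(0.50) = 0.69 |
| 1.5 | 0.50 | Φ(0.707) = 0.76 | Φ(0.25) = 0.60 |
| 1.5 | 0.75 | Φ(0.530) = 0.70 | Φ(0) = 0.50 |

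For d = 1.5, the positive likelihood ratio is 0.773/(1 − 0.773) = 3.4 against healthy controls. It is 0.773/(1 − 0.691) = 2.5 at m = 0.25 and 0.773/0.50 = 1.5 at m = 0.75.

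**Precision with 44 per group.** An observed 35/44 = 0.80 has an exact (Clopper-Pearson) 95% CI of 0.65 to 0.90. An AUC of 0.80 has a Hanley-McNeil standard error of 0.047, so the 95% CI is 0.80 ± 1.96 × 0.047, or 0.71 to 0.89.

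**Role of the 44/44 mix.** Sensitivity is computed within cases and specificity within controls. Neither they, nor the AUC, nor a cut-off maximising their sum is biased by the ratio of the groups. Predictive values do depend on it: PPV = Se·p/(Se·p + (1 − Sp)(1 − p)). With Se = Sp = 0.80, PPV is 0.80 at p = 50%, 0.50 at 20%, 0.31 at 10% and 0.17 at 5%. This matters only if predictive values or overall accuracy are reported, or if the cut-off is chosen by a prevalence-weighted criterion. The plan mentions none of these.

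**The case against.** The strongest reply is that the document claims little. Its endpoints are marker levels, section 5 speaks of relations with the presence and severity of disease, and diagnosis as a purpose appears only in the title. That stands, and it means section 4 needs no change. It does not dispose of the cut-offs, because a cut-off under that title invites diagnostic use.

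A second reply is that the ROC might compare mild with severe L-PrE, where healthy controls play no part. The text does not exclude this. L-PrE versus control fits the title and the primary endpoint better, but the plan should say which is meant.

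A third is that section 5 already concedes an observational design. A cohort of women with suspected disease would also be observational, so the concession does not cover this point.

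Four stronger readings are tempting, and the document does not support them:

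- **That the equal group sizes distort the cut-offs or the AUC.** They do not, as shown above, and no predictive value is planned.
- **That both groups are extremes.** The cases include mild as well as severe L-PrE; only the control side is restricted.
- **That controls were hand-picked.** They are described as randomly selected. The issue is the restriction to uncomplicated pregnancies.
- **That sampling after diagnosis is a separate demonstrated bias.** Section 5 says the women with preeclampsia had no pharmacological treatment, and no additional effect of timing can be shown from the document.

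**Conclusion.** The concern holds in limited form. If the ROC compares L-PrE with control, its results describe separation of established disease from uncomplicated pregnancy. They are likely to be optimistic for women in whom the diagnosis is in doubt, and section 5 does not disclose this. Under the assumed shifts, the AUC falls by 0.05 to 0.15, and specificity at a fixed cut-off falls by 0.08 to 0.27. These sizes rest on the normal equal-variance model and on suspected non-cases having raised markers; with no shift there is no loss. The comparison of marker levels between groups is unaffected. A reader might infer that the study's accuracy figures are invalid because half the sample are cases, but that does not follow.

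**What to change.** **Section 2.** Name the groups entering the ROC. If they are L-PrE and control, state that the cut-offs describe separation of established L-PrE from uncomplicated pregnancy and are exploratory, not diagnostic thresholds. Report AUC, sensitivity, specificity and likelihood ratios with 95% confidence intervals. If predictive values are shown, compute them over a stated prevalence range and not at the 44/44 mix.

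**Section 5.** Add the restriction to uncomplicated controls, and the absence of women with suspected but unconfirmed disease, as a limitation. Word the conclusion as association with the presence of L-PrE rather than diagnosis.

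**Cost.** Rewording and a short recalculation on data already in hand. Recruitment ended in January 2019 and no new patients are needed. The price is a less favourable headline claim.

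### ROC cut-offs for three markers are set in the only sample (44 and 44 women) with no rule or validation stated; accuracy quoted at them would be about 2.5 to 5.5 points optimistic under an optimising rule, and near 0 under an equalising one

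*Combined protocol and SAP*

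**What the plan says.** The only sentence on diagnostic thresholds is in section 2, Baseline Characteristics: "The ROC analysis was applied for determination of cut-off points for IL6, presepsin ve pentraxin-3 variables". It does not name the rule for choosing the threshold or the comparison that the ROC curve serves. The only group comparison named in that section is preeclampsia against control. On software, the section says only "SPSS for Windows 22.0 ve Medcalc programs were used for statistical analysis"; no resampling method is mentioned.

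The sample is given in section 1, Recruitment Details: "The study was conducted with 44 late-onset preeclampsia patients as study group and 44 patients with normal pregnancies as control group". No second cohort, split sample or earlier threshold appears anywhere.

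The title is "Analyses of Interleukin-6, Presepsin and Pentraxin-3 in the diagnosis and severity of late-onset preeclampsia", so diagnosis is a stated aim. The endpoints in section 4 are marker levels by group, beginning with "The primary endpoint in these analyses was IL-6, presepsin and pentraxin-3 levels in L-PrE group and control group". Section 5 concedes "It was a small, observational and single-centered study" and the lack of serial measurements. It does not say that the cut-offs come from the same data and are untested.

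**The concern.** A rule that searches a sample for the best-looking threshold also selects favourable noise. Sensitivity and specificity computed at that threshold in the same women are then too high on average. The threshold itself is also unstable in a sample of this size, and a single reported value hides that.

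At stake is how a reader would use the result. A study with diagnosis in its title that publishes cut-offs invites their use elsewhere. Accuracy quoted at those cut-offs would, on average, not be matched in new patients, and nothing in the plan would warn of it.

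**Working it through.** **Inputs from the document.** 44 cases and 44 controls (section 1). Cut-offs set by ROC analysis, rule not stated (section 2). The document gives no AUC, SD, cut-off, sensitivity or specificity, so there is no stated figure to reproduce.

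**Assumptions, not in the document.** Binormal marker; AUC 0.65 to 0.90; case/control SD ratio r of 0.5 to 2; Youden or closest-to-corner rule.

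**Model.** Controls are N(0, 1) and cases N(δ, r²), with δ = √(1 + r²) × Φ⁻¹(AUC). At cut-off c, true sensitivity is 1 − Φ((c − δ)/r) and true specificity is Φ(c). For AUC 0.75 and r = 1, δ = 1.414 × 0.6745 = 0.954. The best cut-off is δ/2 = 0.477, where sensitivity and specificity are both Φ(0.477) = 68%.

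**Optimism.** In each simulated 44/44 sample the cut-off is chosen from the empirical ROC curve. Optimism is the apparent minus the true value at that cut-off, averaged over sensitivity and specificity. Mean optimism in percentage points per measure (20,000 samples per setting):

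| Rule | SD ratio | AUC 0.65 | 0.75 | 0.80 | 0.90 |
|---|---|---|---|---|---|
| Youden | 1 | 5.2 | 4.7 | 4.3 | 3.5 |
| Youden | 1.5 | 4.6 | 4.2 | 4.0 | 3.3 |
| Youden | 2 | 3.9 | 3.7 | 3.5 | 3.0 |
| Youden | 0.5 | 3.9 | 3.6 | 3.6 | 3.0 |
| Closest-to-corner | 1 | 3.7 | 3.4 | 3.2 | 2.8 |
| Closest-to-corner | 1.5 | 3.6 | 3.3 | 3.1 | 2.8 |
| Closest-to-corner | 2 | 3.4 | 3.1 | 3.0 | 2.6 |
| Closest-to-corner | 0.5 | 3.4 | 3.2 | 3.0 | 2.6 |

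Repeat simulations gave 3.0 to 5.3 (Youden) and 2.5 to 3.8 (closest-to-corner), hence about 2.5 to 5.5 overall. These are averages: apparent accuracy fell below the true value in 9% to 24% of samples. Optimism in the Youden index itself (sensitivity + specificity − 1) is twice the tabulated value.

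**Dependence on the rule and range.** Choosing the cut-off where sensitivity equals specificity gives about 0 to 0.5 points. Taking the lowest cut-off with observed specificity of at least 90% gives 0.9 to 1.4. Outside the assumed range, Youden with equal SDs reaches 5.7 at AUC 0.60. At AUC 0.95, Youden and closest-to-corner give 2.3 to 2.9 with SD ratio up to 2, and 2.0 to 2.2 with SD ratio 3.

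**Sampling error for comparison.** The 95% half-width with 44 women is 1.96 × √(0.25/44) = 14.8 points at a true value of 50%, and 1.96 × √(0.09/44) = 8.9 points at 90%.

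**Instability of the threshold.** At AUC 0.75 with equal SDs, true sensitivity at the chosen cut-off runs from 44% to 86% with Youden and from 55% to 80% with closest-to-corner (5th to 95th percentile), mostly traded against specificity. A repeat run for Youden gave 47% to 88%.

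**Check of the proposed correction.**
- Cross-validation (10-fold, repeated 10 times, cut-off re-selected in each training fold) left at most 0.4 points of bias in either measure in 16 settings. Example, Youden, SD ratio 1, AUC 0.75: apparent index 0.438, cross-validated 0.347, true 0.346. The apparent excess per measure is (0.438 − 0.346)/2 = 4.6 points.
- The root mean squared error (RMSE) of the average of the two measures fell in all 16 settings, for example from 6.6 to 5.5 points (Youden, SD ratio 1, AUC 0.65).
- The RMSE of each measure taken separately mostly rose. In a 12-setting check, specificity worsened in all 12 and sensitivity in most. With Youden, SD ratio 1 and AUC 0.75, sensitivity went from 8.2 to 9.3 points and specificity from 7.9 to 9.3.
- A bootstrap percentile interval for the cut-off covered the population-optimal cut-off in 93% to 98% of data sets. The median spread of true sensitivity across that interval was 14 to 55 points.
- Bootstrap subtraction of optimism was not simulated.

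**The case against.** The strongest reply is that no figure in the document is wrong. It reports no cut-off, sensitivity or specificity and does not commit to any. For harm to follow, three things the document does not say must all be true: an optimising rule was used, accuracy was quoted at the resulting cut-off, and it was quoted uncorrected. The endpoints are group comparisons of marker levels, which this bias does not touch, and neither is the AUC affected. Section 5 already tells the reader that the study is small. All of this stands, and it caps the point at minor.

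One part does not carry the matter away. That the bias is below the sampling error is true, but a confidence interval centred on an optimistic estimate is itself shifted upward, and the plan mentions no such interval.

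Three stronger readings are tempting and are not supported:
- A reader might infer that the study's accuracy is overstated by a known amount. With the rule unstated, the amount could be close to zero.
- A reader might infer that validation was not done. The document is silent; it does not rule out validation or a threshold fixed beforehand.
- The title and the secondary endpoint ("The secondary endpoint was the IL-6, presepsin and pentraxin-3 levels in mild L-PrE group and severity L-PrE group") might suggest a cut-off for severity as well. It would rest on at most 44 women and have larger optimism, but no ROC analysis for that comparison is described.

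**Conclusion.** The concern holds in a conditional form and is minor. Cut-offs are derived in the one sample of 44 and 44, with no rule, prior threshold or validation described. Under Youden or closest-to-corner, sensitivity and specificity quoted in the same women would each be about 2.5 to 5.5 points too high on average, given a binormal marker, AUC 0.65 to 0.90 and SD ratio 0.5 to 2. Those assumptions are the reviewer's. The missing rule is the core of the point, because a reader cannot tell whether the optimism is negligible or about 5 points. It is not evidence that any result in the document is in error.

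**What to change.** The study had closed when the document was dated, so this is a re-analysis of existing data.

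1. State the cut-off rule and the comparison that each ROC curve serves. If a cut-off was fixed in advance, say so; no correction is then needed.
2. Report each AUC with its 95% confidence interval. Report the apparent sensitivity and specificity with their confidence intervals and, beside them, an optimism-corrected estimate that re-selects the cut-off in each resample: stratified 10-fold cross-validation repeated 10 times, or a bootstrap correction. Note that cross-validation describes the selection procedure, and estimates each separate measure at the published cut-off with somewhat more noise. It should therefore accompany the apparent values, not replace them.
3. Give a bootstrap percentile interval for each cut-off, re-selecting it in every resample.
4. Call the cut-offs provisional until tested in an independent sample, and add this to section 5.

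The cost is a short script, with no new patients or assays. The accuracy figures become slightly less favourable, and the corrected estimate of each separate measure is noisier.

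### Does testing three primary markers at an unadjusted 0.05, with no stated success rule, undermine the study's conclusion?

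*Combined protocol and SAP*

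**What the plan says.** Section 4 (Endpoints of the study) sets three ranked endpoints, each built on the same three markers. The first concerns presence of the disease: "The primary endpoint in these analyses was IL-6, presepsin and pentraxin-3 levels in L-PrE group and control group". The next level looks only inside the preeclampsia arm and asks about severity: "The secondary endpoint was the IL-6, presepsin and pentraxin-3 levels in mild L-PrE group and severity L-PrE group". The last level turns to fetal growth, comparing small-for-gestational-age births with the rest on the same markers.

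The tests are in section 2 (Baseline Characteristics). Each variable is compared on its own, by t test or Mann-Whitney U: "Student t test was used for variables that normally distributed for group comparison(L-PrE/kontrol". The tests are named for that contrast only; the severity and SGA contrasts are not mentioned there. The threshold is general: "P<0.05 was accepted as statistical significance". Each marker also gets its own ROC cut-off, which is estimation and not a test.

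Section 5 states the one conclusion in the document: "We demonstrated, significant relations of all three elevated new inflammatory markers with both the presence and the severity of PrE". It reports no SGA finding and no p-values.

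**The concern.** Three co-equal primary markers at 0.05 each, with no decision rule, leave the error rate of the primary endpoint undefined. If one marker is enough, three chances at 5% add up to well over 5%; if all three are needed, they do not. Repeating the markers for severity and SGA gives nine endpoint comparisons with no gate between the levels. The labels primary, secondary and tertiary rank the endpoints but do not control error.

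At stake is the word with which section 5 opens its claim. A reader cannot tell whether joint significance of all three markers was the planned criterion or a pattern noticed afterwards. The document is dated October 2019, recruitment ran to January 2019, and results are already reported, so a prior rule cannot be inferred from it.

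**Working it through.** The plan gives no family-wise error, power or sample-size figure, so there is nothing of its own to reproduce.

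**Inputs from the document.** Per-test level 0.05 (section 2); three markers at each of three endpoint levels (section 4); 44 women per group (section 1). **Assumed:** two-sided tests, one test per marker per endpoint, and the between-marker correlations used below.

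**If any one marker counts.** For k independent tests the error is 1 − 0.95^k.

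- Three primary tests: 1 − 0.95³ = 1 − 0.8574 = 14.3%.
- Presence plus severity, six tests: 1 − 0.95⁶ = 26.5%.
- All nine: 1 − 0.95⁹ = 37.0%.

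These are independence values. The bounds that hold under any dependence are 3 × 0.05 = 15%, 6 × 0.05 = 30% and 9 × 0.05 = 45%. Positive correlation lowers the rates. In simulation at 44 per group with no true difference, any-of-three was 14.2%, 13.8%, 12.7%, 11.0% and 8.4% at correlations 0, 0.3, 0.5, 0.7 and 0.9.

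**If all three must be significant.** The claim is false when at least one marker truly does not differ. All three tests can then succeed only if that marker's test gives a false positive, so the error is at most 5% under any dependence. When no marker differs, simulation gives 0.01% (correlation 0) to 2.4% (correlation 0.9). The same argument covers all three markers for both presence and severity: all six tests must succeed, so the error of that joint claim is again at most 5%.

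**What an adjustment would do to the reported result.** Section 5 reports all three markers as significant for presence and for severity, and section 2 defines that as p below 0.05. Taking these as the section 4 comparisons:

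1. Hochberg at 0.05 on the primary set first compares the largest of the three p-values with 0.05. If it is below, all three are rejected.
2. With the whole primary set rejected, a gate passes the full 0.05 to the severity set.
3. The same step there rejects all three severity comparisons.

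The conclusion is unchanged. Hochberg needs independence or suitable positive dependence.

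**Holm for comparison.** Its thresholds are 0.05/3 = 0.0167, 0.05/2 = 0.025 and 0.05. At 44 per group and 80% power, the detectable differences are 0.70, 0.67 and 0.60 SD. Power for 0.60 SD drops from 80% to 65% at the strictest step. Holm could alter the result: if all three p-values lay between 0.0167 and 0.05, it would reject none, whereas Hochberg would reject all.

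**The case for a change.** The strongest case for acting is that a reported outcome is not a pre-set rule. Had only one or two markers been significant, nothing in the plan would have prevented that from being presented as success. On that view the error rate of the procedure, as opposed to that of the claim that emerged, is the any-one figure. Holm on three existing p-values needs no new data, and nine is a low count, since section 2 adds Spearman correlations and section 3 lists many other group comparisons.

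Part of this stands. The rule is missing, and section 5 does not supply it. But the any-one reading is no better documented than the all-three reading, and it is not the one on which the conclusion rests. The 37% figure pools ranked endpoints into a single family and includes SGA comparisons from which nothing is concluded. It also applies 0.05 to six comparisons for which section 2 names no test.

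A correction chosen now would not restore pre-specification. Selecting Holm over Hochberg, when only Holm could change the reported pattern, would itself be a choice made after the results. Reclassifying severity as exploratory would demote a declared secondary endpoint that is named in the study title, without showing that it fails any test.

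**Conclusion.** The concern does not call for a change. The plan leaves its success rule unwritten, and the primary false-positive risk depends on it: about 8% to 14% if any one marker sufficed (at most 15%), at most 5% if all three were required. The only conclusion stated is of the second kind. On the significance that section 5 reports, it survives Hochberg with a gate from presence to severity. Choosing a stricter correction afterwards is a trade-off against power and not the repair of an error. In a study that describes itself as small, observational and single-centre, reading each of three named markers at a per-test 0.05 is defensible, and the plan never presents that level as family-wise.

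This rests on three assumptions: that section 5 refers to the section 4 comparisons, that its significance means p below 0.05 for every marker in both, and, for Hochberg, that the test statistics are independent or positively dependent. The 5% bound on the joint claim needs no dependence assumption, but it presumes that the claim is judged as an all-or-nothing one. Without p-values the document cannot show how each marker would fare under a stricter correction.

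### Controls were sampled at any routine third-trimester visit and cases probably at about 34+0 to 41+0 weeks, with no adjustment for sampling week: bias is possible, but neither shown nor known in direction

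*Combined protocol and SAP*

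**What the plan says.** Section 1 (Recruitment Details) defines cases as women with "late-onset preeclampsia between 34+0 and 41+0 weeks of gestation". Section 3 (Outcome Measures) says their blood was taken after the diagnosis, in the outpatient clinic; section 5 says the markers were measured only at admission. The week range is therefore stated for diagnosis. That cases were sampled within about the same range is a close inference.

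Of controls, section 1 says: "Pregnant women with uncomplicated pregnancies were randomly selected to serve as controls". Section 3 says: "The samples of the control groups were obtained during the routine obstetrical care examination in the third trimester of pregnancy". Neither statement gives a lower or upper week or mentions matching. Eligibility rests on a reference: "The inclusion criteria were made according to the official documents". Those documents are not reproduced, so a week limit for controls may exist there.

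On analysis, section 2 says: "Student t test was used for variables that normally distributed for group comparison(L-PrE/kontrol"), with Mann-Whitney U for the rest, and "The ROC analysis was applied for determination of cut-off points for IL6, presepsin ve pentraxin-3 variables". Spearman correlation is named for relations among non-normal variables, without saying which. No regression, stratification or covariate-adjusted ROC is named.

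The adjusting variable was collected. Section 3 says: "The demographic data like age, gravidity, parity, body mass index (BMI) and gestational age were recorded". The week of gestation is also on the list of variables compared between groups. Its time point is not given. Sampling or enrolment is the more natural reading, since only infant weight is tied to delivery. The limitations in section 5 do not mention sampling week.

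**The concern.** If controls were on average sampled earlier than cases, and a marker changes with gestational age in normal pregnancy, part of the case-control difference reflects week and not preeclampsia. A marker that rises with week would make the difference and the AUC too large; a marker that falls would make them too small.

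The primary endpoint is this comparison, and the study title claims a role in diagnosis, for which the ROC cut-offs are derived. A cut-off set against earlier controls need not perform as reported in women at 34 to 41 weeks, where it would be used.

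The mild versus severe comparison lies within cases, so the control window does not affect it. It too is unadjusted for week, and cases span seven weeks. The population for the SGA comparison is not stated, so nothing is claimed about it.

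**Working it through.** **What the document fixes.** It gives 44 cases, 44 controls, the case window at diagnosis and P<0.05. It gives no effect size, SD, control sampling weeks or marker-week slope, so there is no planned figure to reproduce.

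**Assumptions, none from the document.** Sampling weeks are uniform: cases 34 to 41; controls 28 to 41, 31 to 41 or 34 to 41. Marker = b × (week − 37) + group effect + normal residual with SD 1. Tests are two-sided at 0.05. The group effect is 0.6 SD, about what 44 per group detects with 80% power: (1.960 + 0.842) × √(2/44) = 0.597.

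**AUC.** The mean case week is 37.5. The mean control week is 34.5 (from 28) or 36 (from 31), so the gap g is 3 or 1.5 weeks. The week variances are 7²/12 = 4.08 for cases, and 13²/12 = 14.08 or 10²/12 = 8.33 for controls; their sum V is 18.17 or 12.42. To a close approximation

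AUC = Φ[(0.6 + b·g) / √(2 + b²·V)].

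For example, with controls from 28 weeks:
- b = +0.15: (0.6 + 0.45)/√(2 + 0.0225 × 18.17) = 1.05/1.552 = 0.677, so AUC = 0.75.
- b = −0.15: (0.6 − 0.45)/1.552 = 0.097, so AUC = 0.54.

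Simulated means agree with the formula to within rounding:

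| Slope b (SD per week) | −0.15 | −0.10 | −0.05 | 0 | +0.05 | +0.10 | +0.15 |
|---|---|---|---|---|---|---|---|
| Controls from 28 weeks | 0.54 | 0.58 | 0.62 | 0.67 | 0.70 | 0.73 | 0.75 |
| Controls from 31 weeks | 0.60 | 0.62 | 0.65 | 0.66 | 0.68 | 0.70 | 0.71 |

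With controls from 34 weeks, g = 0 and the AUC is about 0.66 at every slope.

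**Cut-off (Youden), rising marker, controls from 28 weeks.** As the slope goes from 0 to 0.15, actual specificity in controls at 34 to 41 weeks falls from about 59% to 49%, and actual sensitivity rises from about 63% to 72%. The actual Youden index hardly moves: 0.59 + 0.63 − 1 = 0.22 and 0.49 + 0.72 − 1 = 0.21 from the rounded figures. Apparent specificity is 63% to 67%. At slope 0 it already exceeds the actual value by about 5 points, the usual optimism of a cut-off chosen on the same data; at slope 0.15 the excess is about 67 − 49 = 18 points.

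**No true difference.** Mann-Whitney false positives per marker at slopes 0 / 0.05 / 0.10 / 0.15 are 5% / 10% / 25% / 46% (28 weeks), 5% / 6% / 10% / 16% (31 weeks) and about 5% (34 weeks). All three markers are falsely elevated in at most 12.7% of datasets with independent residuals, or 23% with residual correlation 0.5. Both maxima need 28-week controls and the steepest slope.

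**What the planned week comparison catches.** If it refers to week at sampling, Mann-Whitney flags the imbalance in 97% (28 weeks) or 69% (31 weeks) of datasets. In the 31% of 31-week datasets that go unflagged, the AUC at positive slopes is still 0.68 to 0.69 against 0.66.

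**The case against.** A reader might infer that the three elevated markers in section 5 are an artefact of gestational age, or that the AUCs are inflated. The document supports neither. It does not say that controls were sampled earlier or that any marker rises with week. If the markers fall with week, the reported elevation is conservative. Three falsely elevated markers with the week imbalance unflagged occurred in at most 0.25% of simulated datasets.

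The other side has more. Gestational age was recorded and compared between groups, so a large imbalance would probably be seen, and the AUC error left in unflagged 31-week datasets (0.02 to 0.03) is small beside the AUC's own sampling SD of about 0.058. The official documents behind the inclusion criteria may restrict control weeks, which would remove the issue. The study declares itself small and observational. With a rising marker, the cut-off trades specificity for sensitivity and loses little actual discrimination.

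All of this stands, and it limits the weight of the point. It does not close the gap: seeing an imbalance warns the reader but corrects neither the marker difference nor the reported AUC, and nothing in the document says what follows if an imbalance is found. Spearman correlation, even if run against week, would not adjust the group comparison.

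**Conclusion.** The gap in the text is certain: no week limits or matching are stated for controls, and no adjustment is named for the primary comparison or the ROC. Whether bias occurred, how large it was and in which direction cannot be determined. Under the assumed model the range runs from understatement (AUC 0.54 against 0.66) through none to overstatement (0.75), and both extremes need controls from 28 weeks with a steep slope. Where markers rise with week, what is overstated is chiefly the apparent performance of the cut-off. These sizes rest wholly on assumed sampling weeks, a linear trend and a true difference of 0.6 SD. The point is minor: a reporting gap with an inexpensive improvement.

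**What to change.** 1. Report gestational age at blood sampling by group (median, range, number of controls below 34+0), and state the time point of the week of gestation that was compared. If only the delivery week was kept, the sampling week can be rebuilt, since "The gestational age was determined by calculation from the last menstrual period"; this assumes that sampling dates are on file.
2. Beside the unadjusted results, and labelled post hoc, add a regression of each marker (log-transformed if skewed) on group and gestational age at sampling, with 95% CI. Add a covariate-adjusted ROC, or a ROC restricted to controls sampled at 34+0 or later, as a sensitivity analysis. If all controls are already at 34+0 or later but the medians differ, restriction changes nothing and the adjusted forms are needed.
3. If the sampling weeks differ materially, base the case-control conclusion and cut-offs on the adjusted analysis and add the point to the limitations. Judge this from the reported distributions, not from one early control or from P<0.05 alone. If the weeks are aligned, say so and let the unadjusted results stand.

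**Does it work?** In the simulations without a true difference, week-adjusted regression held false positives at 4.7% to 5.2%. With the 0.6 SD difference and slopes of 0 or above, the restricted ROC gave an AUC of 0.657 to 0.665, and a ROC on week-adjusted residuals 0.661 to 0.665.

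**Cost.** No new patients or assays are needed. Recruitment ended in January 2019 and results are already stated, so the reanalysis cannot be presented as prespecified. At a true 0.6 SD and slope 0, power falls from 80% to 70% (28-week controls) or 76% (31-week), and only to 79% if weeks are aligned. Restriction costs more: Mann-Whitney power falls from 77% to 61% or 69%, with on average 24 or 31 of the 44 controls kept, and the optimism in cut-off specificity rises from about 5 points to about 8 or 6. That is why adjustment is preferred and restriction is kept as a sensitivity analysis.
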